## **1. INTRODUCTION AND OBJECTIVES OF ANALYSIS**

### **1.1. Introduction**

Study RP103-MITO-002 was closed prematurely after decision by the Sponsor to end development of RP103 for mitochondrial disease. This statistical analysis plan (SAP) describes the safety analyses that will be performed for Study RP103-MITO-002, based on the study protocol dated 16DEC2014.

### **1.2. Study Objectives**

The primary objective is to assess safety, tolerability and efficacy of long-term repeat dosing of RP103 in subjects with inherited mitochondrial disease.

The secondary objective is to assess the steady-state pharmacokinetics (PK) and pharmacodynamics (PD) of RP103 at steady state, in children with inherited mitochondrial disease.

## **2. STUDY DESIGN**

### **2.1. Synopsis of Study Design**

This is an open-label extension study of RP103-MITO-001 to assess the safety, tolerability, and efficacy of Cysteamine Bitartrate Delayed-release Capsules (RP103) for treatment of children with inherited mitochondrial disease.

Subjects who have completed all visits associated with Study RP103-MITO-001 will be offered enrollment in this extension study. If enrolled in RP103-MITO-002, subjects will return to the clinic quarterly (every 3 months) for detailed assessments.

Study visits will occur as follows:

Day 1 (Baseline): is the day of enrollment, and will occur simultaneously with the RP103-MITO-001 Study Exit Visit.

Quarterly Visits: will begin within 3 months ( $\pm 7$  days) of the RP103-MITO-002 Day 1 Visit and will continue quarterly (every 3 months).

Study Exit Visit: will take place upon study completion (i.e. marketing approval has been granted for RP103 and the subject is able to obtain in commercially), study termination, or upon individual subject termination.

The maximum treatment time in the study is estimated to be 24 months.

Upon RP103-MITO-002 study entry, subjects will continue on the last total daily dose of RP103 taken during the previous RP103-MITO-001 study. Subsequent RP103 dose adjustments are permitted (e.g. as the subject grows, or if deemed necessary by the Investigator for tolerability reasons).

The Sponsor's medical officer may be consulted for assistance making RP103 dose adjustment decisions at any time during the study. NOTE: For each subject, when calculating the number of

capsules to be taken every 12 hours (i.e. half of the prescribed total daily dose), if rounding is required to get a whole number of capsules to be taken, then rounding should be down and not up.

## **2.2. Randomization Methodology**

As this is an open label study with a single test drug, no randomization methodology is employed.

## **2.3. Stopping Rules**

Close monitoring of the subjects during the study is performed. Any decision to stop the clinical trial is immediately communicated to all Investigators and to the United States FDA and regulatory authorities of any other participating countries.

### **Individual subject dosing is stopped if:**

- A subject exhibits a treatment-emergent adverse event of Common Terminology Criteria for Adverse Events (CTCAE) Grade 3 or higher and not likely related to the underlying disease, and possibly, probably or definitely related to study drug.

### **A subject is discontinued if they exhibit an:**

- Unexplained fever ( $> 38.5^{\circ}\text{C}$ ) for  $> 24$  hours.

### **The study is halted and FDA (or participating regulatory authority) will be consulted if:**

- Two or more subjects develop the same CTCAE Grade 3 adverse event;
- One subject develops a CTCAE Grade 4 adverse event;
- One or more unexpected drug-related deaths.
- Onset of one or more drug-related cases of:
  - Heart failure (NYHA Class II or greater);
  - Respiratory failure (Type 1 or Type 2);
  - Acute liver failure (associated with an international normalized ratio (INR) of greater than 1.5, and any degree of mental alteration (encephalopathy) in a subject without preexisting cirrhosis);
  - Malignant hypertension (i.e., Diastolic blood pressure  $> 140$  mmHg);
  - Nephrotic syndrome which includes protein in the urine (more than 3.5 grams per day) and one or more of the following clinically significant symptoms: low blood protein levels and/or high cholesterol levels and/or high triglyceride levels and/or edema.

## **2.4. Study Procedures**

The schedule of assessments, as outlined in the study protocol, is provided in **Table 1**.

**Table 1      Schedule of Assessments**

PROCEDURE	Baseline Day 1	Quarterly Visits Every 3 months	Study Exit
Allowable Visit Window	None	+/- 7 days	+/- 7 days
Informed Consent	X		
Assess/Confirm Eligibility	X		
Enrollment	X		
Medical and Medication Histories	X		
Monitoring of Adverse Events	X	X	X
Adverse Events Checklist	X	X	X
Review of Concomitant Meds	X	X	X
Vital Signsa (including body temperature)	X	X	X
Height, Weight, Head Circumferencea	X	X	X
BMI / BSA Calculationsa	X	X	X
12-lead ECGa	X	X	X
Physical Examinationa	X	X	X
Clinical Laboratory Testsa,b	X	X	X
Serum Pregnancy Test a(if applicable)	X	X	X
Breath Samples for Hydrogen Sulfidea	X	X	X
PD Biomarker Sample Collection b,c	X	X	X
PK Sample Collection c	X	X	X
Record Seizure Activityd	X	X	X
Subject Diary Training/Dispense	X	X	
Subject Diary Collect/Review/Sign	X	X	X
RP103 Administration	X	X	X
Dispense and / or Collect RP103e	X	X	X
Administer age-specific NPMDS	X	X	X
Conduct two of the following assessments, already specified during participation in previous Study RP103-MITO-001:			
6-minute Walk Test ; Jama Dynamometer	X	X	X
Barry-Albright Dystonia Scale	X	X	X
Friedreich Ataxia Rating Scale	X	X	X
Modified Lansky Play Performance Scale	X	X	X
Gross Motor Function Measure	X	X	X
Vision/Eye Examination	X	X	X

**Schedule of Events Footnotes**

a RP103-MITO-001 Study Exit is to take place on the same day as RP103-MITO-002 Day 1 (Baseline). Data collected from the RP103-MITO-001 study (i.e. medical history, ongoing adverse events, concomitant

medications, Study Exit vital signs) may be carried forward to the extension study clinical database. Data recording and entry instructions will be supplied via the electronic CRF instructions.

- b Clinical Laboratory Tests and PD Biomarkers are specified in Protocol Table 2; Samples for Clinical Laboratory Tests and PD Biomarkers should be collected at the same time as PK blood samples.
- c PK blood samples will be collected within 30 minutes before or after the RP103 morning dose.
- d Seizure activity may be recorded by patients/caregivers using a paper seizure diary handed out by the site, or the form provided on [www.seizuretracker.com](http://www.seizuretracker.com) website. If patients use the web-based form, it must be printed out and used as source documentation for any associated CRF data entry.
- e RP103 from the previous Study RP103-MITO-001 must be taken for the morning dose and associated PK blood draws on the day of Study Exit. Then, RP103 for Study RP103-MITO-002 is to be dispensed for the evening dose (RP103-MITO-002 Day 1) and to be taken every 12 hours for the remainder of participation in Study RP103-MITO-002.

## **2.5. Safety Variables**

The safety profile of RP103 will be investigated through analysis of the following safety assessments: clinical laboratory tests, vital signs, physical examination, 12-lead ECG, urinalysis, serum pregnancy, concomitant medications, and subject incidence of treatment-emergent adverse events.

## **3. SUBJECT POPULATIONS**

### **3.1. Population Definitions**

The following analysis population will be used.

#### **3.1.1. Safety Analysis Set (SAF)**

The safety analysis set (SAF) is defined as all subjects who received at least one dose of study drug (RP103).

The SAF is the primary population for the analysis of safety endpoints.

### **3.2. Protocol Deviations**

The following protocol deviations will be recorded and summarized in the final report: 1) eligibility (inclusion/exclusion) violations, 2) study drug dosing violations, 3) excluded medication violations, 4) procedures performed outside the protocol-specified window, 5) procedures not done, 6) subject non-compliance and 7) other, to be specified by the Investigator. All protocol deviations will be presented in a by-subject data listing.

## **4. STATISTICAL METHODS**

### **4.1. Sample Size Justification**

The sample size will be up to 35 subjects (the number of subjects dosed in study RP103-MITO-001).

### **4.2. General Statistical Methods and Data Handling**

#### **4.2.1. General Methods**

Tabulations will be produced for appropriate demographic, baseline, and safety parameters. For categorical variables, summary tabulations of the number and percentage within each category (with a category for missing data) of the parameter will be presented. For continuous variables, the mean, median, standard deviation, minimum and maximum values will be presented. Additional statistics may be presented for certain endpoints as described in the sections below.

All output will be incorporated into Microsoft Excel or Word files, sorted and labeled according to the International Conference on Harmonisation (ICH) recommendations, and formatted to the appropriate page size(s).

#### **4.2.2. Computing Environment**

All descriptive statistical analyses will be performed using SAS statistical software (Version 9.2 or later), unless otherwise noted. Adverse Events will be coding using MedDRA version 17.0 or later. Concomitant medications will be coded using World Health Organization (WHO) Drug (June 2013).

#### **4.2.3. Methods of Pooling Data**

Not applicable to the present study.

#### **4.2.4. Adjustments for Covariates**

No formal statistical analysis that adjusts for possible covariate effects is planned.

#### **4.2.5. Multiple Comparisons/Multiplicity**

Multiplicity is not of concern for this exploratory study with a descriptive interpretation.

#### **4.2.6. Withdrawals, Dropouts, Loss to Follow-up**

Subjects will be informed that they are free to withdraw from the study at any time and for any reason. The Investigator may withdraw a subject from the study if, in the Investigator's opinion, it is not in their best interest to continue participation. Notification of early termination will immediately be made to the Sponsor's representative(s).

In case of early termination the subject must return to the clinical for a Study Exit visit within 4 weeks after last dosing (28 days +/- 7 days) and perform all assessments detailed in the Schedule of Events (**Table 1**). The reason for discontinuation will be recorded in source documentation and the eCRF.

Subjects may be withdrawn from the study for the following reasons:

- Adverse event(s);
- Pregnancy;
- Withdrawal of consent;

- Subject non-compliance;
- Investigator decision;
- Sponsor decision, i.e., cancellation of drug development;
- Request from regulatory agency (e.g. FDA), Institutional Review Board, or Ethics Committee.

#### **4.2.7. Missing, Unused, and Spurious Data**

In general, there will be no substitutions made to accommodate missing data points. All data recorded on the CRF will be included in data listings that will accompany the clinical study report.

#### **4.2.8. Visit Windows**

It is expected that all visits should occur according to the protocol schedule. All data will be tabulated per the nominal visit as recorded in the database. In data listings, the relative day of all dates will be presented. Relative days will be calculated relative to the first dose of study drug. Day 1 will be the first day of study drug administration in the study, and the day prior to the first dose of study drug administration will be Day -1. There will be no Day 0.

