#### 10.5. Blood Volume

Assuming participation of the entire 24 months study, the estimated volume of blood drawn (in mL) per subject is provided below. If the Investigator suspects alcohol or drug abuse, or deems that additional lab tests are required for the follow-up of an adverse event, more blood samples may be collected.

Study Visit	Maximum # Visits	Chemistry & Hematology	PK	PD	Pregnancy	TOTAL without pregnancy tests	TOTAL with pregnancy tests
Day1 Visit	0 mL (blood was collected at previous Study RP103-MITO-001 Study Exit Visit)						
Quarterly Visit	7	4.5 mL	2 mL	4 mL	0.5 mL	73.5 mL	77 mL
Study Exit Visit	1	4.5 mL	2 mL	4 mL	0.5 mL	10.5 mL	11 mL
						84 mL	88 mL

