#### **4.6.3.      Laboratory Data**

Clinical laboratory values will be expressed using the International System of Units (SI) units.

The actual value and change from baseline to each on study evaluation will be summarized at all visits using descriptive statistics for each clinical laboratory parameter, including hematology, clinical chemistry and urinalysis.

All laboratory data including hematology, chemistry, urinalysis and serum pregnancy will be provided in data listings.

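### Laboratory and vital-sign summaries go by nominal visit alone, so the event-driven Study Exit column mixes times since Day 1, and no last-value or worst-value summary compensates

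*SAP*

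**What the plan says.** - **Visit rule.** SAP 4.2.8 states: "All data will be tabulated per the nominal visit as recorded in the database". It defines no analysis windows. It does derive a relative day for every date, but for the listings.
- **Laboratory data.** SAP 4.6.3: "The actual value and change from baseline to each on study evaluation will be summarized at all visits". No last-value, worst-value or shift table is described.
- **Vital signs.** SAP 4.6.4 plans value and change at each evaluation, again with nothing else.
- **ECG and neurological examination.** SAP 4.6.6 plans shift tables at each visit and at the last observed value. SAP 4.6.5 plans a shift to the last observed value.
- **Study Exit.** SAP 2.1 ties it to commercial availability after marketing approval, "study termination, or upon individual subject termination". On duration it says: "The maximum treatment time in the study is estimated to be 24 months".
- **Closure.** SAP 1.1: the study was "closed prematurely after decision by the Sponsor to end development of RP103 for mitochondrial disease".
- **Protocol commitment.** Protocol 12.1 foresees descriptive tables of both change and shift from Baseline for the safety laboratory variables, and names vital signs and ECGs in the same sentence. SAP section 5, which lists the analyses not performed, mentions no laboratory or vital-sign shift table.
- **Unscheduled samples.** Protocol 10.5 allows extra blood samples if the investigator "deems that additional lab tests are required for the follow-up of an adverse event". The SAP does not say how such values are summarized. SAP 4.2.7 puts all CRF data in listings.

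**The concern.** A by-visit mean change is interpretable when everyone in the column has been followed for about the same time. The quarterly columns meet that condition and the Study Exit column does not. A subject who left at month 4 and one who left at month 20 enter it with equal weight. The month 4 value is also not counted in the Month 3 column, although it is the nearest one. Quarterly columns therefore omit values that were measured at about the right time, and the Exit column has no defined time.

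A last-value or worst-value table would make up for much of this. The SAP uses the last observed value for ECG and neurological examination but not for laboratory data or vital signs. Protocol 5.3 mentions occasional reversible leucopenia and abnormal liver function studies with cysteamine. Visit means are a weak way to show a reversible change in a few subjects; a worst-value or shift table is the usual one. Safety is all that this SAP reports, so the form of these tables matters more than it would beside an efficacy analysis.

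**Working it through.** **1. The plan's own visit count.** Protocol 10.5: 24 months / 3 months = 8 post-baseline visits, that is 7 quarterly plus 1 Study Exit. Blood volume agrees: 4.5 + 2 + 4 = 10.5 mL per visit; 7 x 10.5 = 73.5 mL; 8 x 10.5 = 84 mL. The plan's figures reproduce. Even a subject who stays the full 24 months has the eighth value labelled Study Exit, so no quarterly column runs past Month 21.

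**2. Permitted timing of an exit value.** It can fall shortly after Day 1, or as late as 24 months + 7 days = 24 + 7/30.44 = 24.2 months. After early termination, SAP 4.2.6 places the visit 28 +/- 7 days after the last dose, which is 21 to 35 days off drug. With a last dose at month 24, that gives up to 24 + 35/30.44 = 25.1 months.

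**3. Summaries described, side by side.**

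| Data | By visit | Last value | Worst value | Shift |
|---|---|---|---|---|
| Laboratory (4.6.3) | yes | no | no | no |
| Vital signs (4.6.4) | yes | no | no | no |
| ECG (4.6.6) | yes | yes | no | yes |
| Neurological (4.6.5) | no | yes | no | yes |

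**4. Illustration of size.** The inputs are assumptions, because the documents give neither enrolment nor closure dates: N = 35 (the SAP 4.1 maximum), even enrolment over A months, common closure C months after the first enrolment, no other dropout, all exits on treatment. Exit times are then uniform from C - A to C.

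- Expected spread of exits = A(N - 1)/(N + 1).
- Quarterly count at month q if the visit is held and the exit follows = N(C - q)/A.
- The same count if an exit within 1.5 months replaces the quarterly visit = N(C - q - 1.5)/A.
- Count after assigning exits to the nearest quarter = N(C - q + 1.5)/A.

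| A, C | Spread (months) | q | Visit held | Exit replaces visit | After windowing |
|---|---|---|---|---|---|
| 6, 12 | 6 x 34/36 = 5.7 | 9 | 17.5 | 8.75 | 26.25 |
| 12, 18 | 12 x 34/36 = 11.3 | 12 | 17.5 | 13.1 | 21.9 |
| 18, 24 | 18 x 34/36 = 17.0 | 12 | 23.3 | 20.4 | 26.25 |

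Windowing adds N x 1.5/A subjects to a mid-study column if the visit is held (8.75, 4.4 and 2.9), and twice that if the exit replaces it (17.5, 8.75 and 5.8). In the first case an equal number, N x 1.5/A, have two values in one window, so a selection rule is needed. With the protocol's N = 25, A = 12 and C = 18, Month 12 goes from 12.5 or 9.4 to 25 x 7.5/12 = 15.6.

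**5. Window edges.** With targets at 91 x k days +/- 45, the first window opens on day 91 - 45 = 46. An exit before Day 46 would have no window unless the first one is extended.

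**The case against.** The case for leaving the plan alone is substantial. The analysis is descriptive, has no formal hypothesis testing, covers at most 35 subjects and feeds an abbreviated report after development ended. Tabulating by nominal visit is a disclosed choice. No value is lost: exit values are in their own column and are listed with their study day. The mixing follows from the event-driven exit and would exist without early closure. SAP section 6 carries no table list in the public text, so the table shells may contain more than the methods section says. All of this stands and limits the weight of the point; it does not supply the missing summaries.

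Four stronger readings are tempting and are not supported:

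- *That all safety data are tabulated only by nominal visit.* ECG and neurological examination have last-observed-value tables, and adverse event and exposure summaries are not visit-based.
- *That unscheduled values enter no table.* The SAP is silent; it does not exclude them. Its wording for laboratory data and vital signs could cover them, and an unscheduled ECG could be the last observed value.
- *That transient laboratory toxicity is missing from every table.* Protocol 10.4 requires a clinically significant abnormal result to be recorded with its adverse event in the eCRF, and SAP 4.6.2 tabulates treatment-emergent events. The extra samples in Protocol 10.5 are for following an event that should already be reportable.
- *That the missing-data category in SAP 4.2.1 dilutes late-visit percentages abnormal.* That category applies to categorical variables, and no by-visit percentage abnormal is described for laboratory data or vital signs. The by-visit ECG shift table is described as numbers of subjects.

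One further objection shapes the remedy. Windowing every exit value would move values taken 21 to 35 days after the last dose into quarterly columns of on-treatment values. Only on-treatment exit values should be windowed.

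**Conclusion.** The point holds for laboratory data and vital signs. Their Study Exit column has no defined time since Day 1, exit values are absent from the quarterly columns they match, and no last-value, worst-value or shift summary compensates. The absence of the protocol's laboratory shift tables from both the methods and the list of dropped analyses is a separate, documented gap. The handling of unscheduled values is unstated, which is a gap in specification and not evidence that they are left out.

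The size is not known. The figures in the working illustrate what assumed enrolment and closure dates would produce; they do not estimate this study. The spread and the gain would also change with individual withdrawals, and the gain shrinks with every exit value taken off drug. This is a minor improvement to a descriptive safety report, and it does not call any conclusion into question.

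**What to change.** 1. **SAP 4.6.3 and 4.6.4.** For each laboratory and vital-sign parameter, add the last on-treatment value and the worst on-treatment value, or shift from baseline to each, with unscheduled values included. State the direction of worst (highest, lowest or both) for each parameter, and define on treatment by the date of last dose. If laboratory shift tables are not to be produced, say so in SAP section 5.
2. **SAP 4.2.8.** Assign Study Exit values taken on treatment to the nearest quarterly window by relative day, for example a target of 91 x k days +/- 45. Extend the first window back to cover exits before Day 46. Where a subject has two values in one window, use one by rule, for example the closest to target. Show exit values taken after the last dose in a separate post-treatment row.
3. **Unscheduled values.** State in 4.2.8 that they count towards the last and worst summaries, and whether they can fill a quarterly window.

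The cost is SAP wording, one derived visit variable (relative day already exists for the listings) and the added rows. Windowed visits will differ slightly from CRF labels and need a footnote. The last-value row still mixes durations, but it is labelled as such. A worst value tends to be more extreme the longer a subject is followed, so both should be read beside the exposure table in SAP 4.6.1.

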#### **4.2.9. Baseline Definitions**

For all endpoints involving a baseline measure, baseline will be the value obtained at day 1.

#### **4.3. Interim Analyses**

No interim analyses are planned for this study.

#### **4.4. Subject Disposition**

Subject disposition will be tabulated, including the number of subjects enrolled and treated, the number of subjects that withdrew prior to completing the study and primary reasons for withdrawal, as well as the number of subjects in the Safety Analysis Set.

A by-subject listing of study completion information, including the reason for premature study withdrawal, if applicable, will be presented.

#### **4.5. Demographic and Baseline Characteristics**

Demographic, baseline characteristics, mitochondrial disease subtype, and medical history is summarized using descriptive statistics and presented for the SAF.

Age, height, weight, body mass index (BMI), and body surface area (BSA) will be summarized using descriptive statistics (number of subjects, mean, standard deviation, median, minimum, and maximum). The number and percentage of subjects by sex and racial/ethnic category will also be presented.

All collected demographic, baseline characteristic, and medical history data will be provided in data listings.

## **4.6. Safety Analyses**

Safety analyses will be conducted using the Safety Analysis Set.

### **4.6.1. Study Drug Exposure**

Descriptive statistics will be presented for total duration of exposure in days, computed as the last dose - first dose + 1. Duration of exposure will also be summarized in weeks by dividing the exposure in days by 7. Additionally, the number and percent of subjects completing dosing through duration categories ( $\geq 1$  day,  $\geq 12$  weeks,  $\geq 24$  weeks, etc.) will be presented.

Dosing compliance will be assessed by tabulating the number of days in which a subject missed a dose up through date of study discontinuation. All dosing data will be presented in a data listing with a record for each dosing event as documented on the subject daily diaries and in-clinic administration records.

